Patients will have the opportunity to speak with researchers in several ways. Patients may be contacted by a member of the research study team by phone, text, email, or in-person (during routine visit to the treatment center) and asked if they are interested in hearing about a study that is testing a new intervention to help people stay in treatment. Alternatively, patients may be given the opportunity to view a pre-recorded video of the team introducing the study and inviting the participant to contact the research

team by phone to indicate their interest to participate. This video will be made available on a computer located in a sanitized, private room at the treatment center during patients' routine visits to UMDTC. Interested individuals will also have the opportunity to write their name and contact details on a research study flyer at dosing and to deposit this flyer in a secure lockbox for the research team to contact them. The research team will screen and flag eligible individuals who should receive this flyer at dosing using the treatment center's HIPAA compliant softwares, Methasoft and EPIC. Researchers will use the same flagging system to indicate participants who should be informed of researcher on-site presence for in-person description of the research opportunity, when applicable.

Patients who are currently pregnant based on initial chart review will be considered ineligible for the study. Eligible patients who begin the study and become pregnant while enrolled will remain engaged in the study. Each participant will be engaged in the study for a maximum period of approximately three months; during this period, we do not expect early pregnancy (i.e. in the first trimester) to affect study participation and the intervention presents no additional risk to pregnant women. Standard procedures for pregnancy care at UMDTC will be followed and participants will be referred for subsequent care as needed (which typically begins starting in later pregnancy) following the three months of participation in this study. Patients will also be informed that the study provides gift card compensation, that their participation is voluntary, and that participation has no impact on their treatment at UMDTC or at any other location.

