### **Intervention and Assessments**

Following completion of the baseline assessment, the participant can meet with the PRS for up to 12 BA sessions (5 core content sessions and 7 review sessions) that can be scheduled based on individual treatment plans and particular participant needs based on distinct methadone dosing schedules, with the aim of a minimum session frequency of every other week. These sessions will be held either remotely or in-person at the drug treatment center, depending on participant availability and preference. Based on participant needs and preferences, the PRS may provide a second check-in between BA sessions. The additional check-in will focus on challenges and barriers that participants are experiencing in their methadone treatment. These sessions can be conducted via phone (including telephone, Zoom, or Google Voice), videoconference (Zoom), or in-person at the drug treatment center. Participants can conduct remote sessions from their homes or other preferred private locations. In-person sessions will take place at 1001 (the drug treatment center) and follow all UMDTC COVID-19 precautions for in-person interaction at this site.

The study interventionist will be a trained and supervised PRS who will receive training in protocol and intervention procedures. Supervision session between the PRS and a research team member (overseen by a licensed clinical psychologist on the research team) will take place approximately weekly. The peer hired as the study interventionist will be a Maryland Certified Peer Recovery Specialist (CPRS). CPRS certification is managed by Maryland Department of Health and requires 46 hours of training, 500 work hours in peer recovery support, and 25 hours of documented supervision under a registered peer supervisor.

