In order to assess MOUD retention and treatment adherence, we will extract routinely-collected data from patient medical charts (maintained by UMDTC) at each BA session and assessment, with collected data consisting of MOUD intake date, clinic attendance, counselor appointments, dosing, dose volume, any notes on patient dosing, any breathalyzer results, any urinalysis or other drug testing results, and we will ask participants about any changes to their enrollment in treatment programs. This use of medical records is outlined in the consent form. At each BA session, participants will complete two items on the Ira Wilson's Self Report Adherence Measure.

During the approximately weekly or biweekly sessions, the PRS will determine the participants' specific circumstances and needs and will draw upon intervention components accordingly. Intervention components can include: Life Steps to identifying and overcoming day-to-day barriers to treatment, SMART goal identification and work, case management with the treatment facility, and modified Behavioral Activation (BA) to support retention in treatment. The PRS will complete/update the intake goals and follow-up goals with the participant during sessions to keep track of the participants' individual plans moving forward. PRS can also work through BA modules during sessions and review material as needed. After sessions, the PRS will complete a fidelity assessment to indicate which components were addressed. Specifically, the approach can focus on the following six elements: (1) psychoeducation regarding substance use, (2) treatment rationale, (3) identification of treatment barriers and solution planning, (4) identification of valued life areas to guide activity selection, (5) monitoring of current activities, (6) scheduling of new activities, and (7) tracking of actual behaviors and subsequent substance use behaviors.

If a participant misses BA sessions and/or dosing, the PRS will continue to follow up with the participant to assess barriers, concerns, and try to continue treatment.

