After completing the posttreatment assessment (approximately 3 months after baseline), participants will be invited to complete a qualitative exit interview which will ask them about their experience in the treatment. Exit interview can take place by phone, video, or in-person. Participants who have dropped out of the program early will also be invited to complete the midpoint assessment, posttreatment assessment, and exit interview over the remaining period of the planned study timeframe (an intent-to-treat approach) or at their earliest convenience. The exit interview will take place immediately following the posttreatment assessment or may be scheduled within approximately one week. Because this interview will ask about the participants' experiences with the PRS, the interview will be conducted by a trained member of the study staff and the participants' responses will not be shared with the PRS. The participant will be asked for their consent for the interview to be recorded. They will be assured that audio recording will be used for research purposes only. The recording will be uploaded to UMCP's Box folder immediately following the session, and the audio file will be deleted from the recording device.

As stated above, posttreatment assessment will take place at approximately three months after baseline, at which point participants who have not yet completed 12 intervention sessions may choose to continue meeting with the interventionist approximately weekly until they reach a maximum of 12 sessions or until they choose to discontinue intervention (whichever occurs first). Those participants will be offered another, optional posttreatment assessment and exit interview, also compensated with \$25 and \$15 gift cards (respectively).

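### Do the $260 compensation maximum and the three-month limit on participation, which other parts of the protocol exceed, call for a change to the plan?

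*Protocol*

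**What the plan says.** **Length of participation.** Under Recruitment and Screening the protocol states: "Each participant will be engaged in the study for a maximum period of approximately three months". The same paragraph uses that period when it discusses participants who become pregnant after enrolment: "we do not expect early pregnancy (i.e. in the first trimester) to affect study participation", with referral for later care placed "following the three months of participation in this study".

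Under Intervention and Assessments, participants may have up to 12 sessions, "with the aim of a minimum session frequency of every other week". The posttreatment assessment falls at about three months after baseline. At that point "participants who have not yet completed 12 intervention sessions may choose to continue meeting with the interventionist approximately weekly", and they may do so "until they reach a maximum of 12 sessions or until they choose to discontinue intervention". The text adds: "Those participants will be offered another, optional posttreatment assessment and exit interview". The same section pays $5 for each weekly confirmation of contact details, for up to 24 weeks.

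**Compensation.** The Risks section lists $80 for the standard assessments and exit interview, $60 for 12 sessions and $120 for 24 contact checks. It mentions a further $40 for those offered the second posttreatment assessment and interview. It then gives $260 as the most a participant can receive after completing everything.

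**The concern.** A stated maximum should cover whatever the protocol permits, and on a plain reading neither of these does. The $260 is described as the total with every assessment completed, yet a paid assessment and interview mentioned just before it are not in the sum. The figure also stands in the paragraph on coercion risk, directly before the judgement that the payments are proportionate.

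The three-month limit is contradicted more directly, because sessions and a second assessment can follow the three-month assessment. Two remarks about pregnancy refer to that period. If participation runs longer, they may not describe every participant who becomes pregnant and also extends. A reader could reasonably ask whether the burden, the payments and the safety reasoning were all set out for the same length of study.

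**Working it through.** **Compensation.** All inputs are in Intervention and Assessments and in Risks.

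- Baseline, midpoint, posttreatment and exit interview: 25 + 15 + 25 + 15 = $80.
- Sessions: 12 × 5 = $60.
- Contact checks: 24 × 5 = $120.
- Sum: 80 + 60 + 120 = **$260**. This reproduces the stated maximum exactly.
- Optional second posttreatment assessment and exit interview: 25 + 15 = $40.
- Sum with the optional items: 260 + 40 = **$300**. The omission is 40/300 = 13% of that total.

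The $260 is therefore right for a participant who does not take the second assessment and interview, and $40 low for one who does.

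**Does the $260 fit a three-month study?** Take three months as 13 weeks with one contact check a week. The checks then pay 13 × 5 = $65, and the total is 80 + 60 + 65 = $205. So the $260 already supposes about 24 weeks of contact, or roughly 5.5 months. Whether a weekly contact check counts as being engaged in the study is not defined. The protocol presents the checks as a tracking incentive, not as sessions or assessments. That part is an ambiguity, not a contradiction.

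**How far can sessions run?** The protocol expects a range of attendance: "During the approximately weekly or biweekly sessions".

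- Weekly attendance: 12 sessions are done by about week 12, and no extension is needed.
- Every other week: 6 sessions by week 13 (weeks 2 to 12) or 7 (weeks 1 to 13). That leaves 12 − 6 = 6 or 12 − 7 = 5. Held weekly, these end at week 13 + 6 = 19 or 13 + 5 = 18.

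The week 18–19 figure is illustrative. No calendar limit is given, but the cap of 12 sessions at an approximately weekly pace bounds the extension in practice.

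**What depends on these sentences?**

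- *Benchmarks.* Feasibility is a percentage agreeing to participate or attending the first session. Acceptability is a percentage completing at least 75% of the five core sessions. Fidelity is rated on a random 20% of sessions. None uses a payment total or the three-month sentence, and neither document ties the core-session count to a calendar window.
- *Data collection.* The scheduled posttreatment assessment stays at about three months after baseline for everyone. The optional one is additional and replaces nothing.
- *Sample size.* The targets of 30 starting the intervention and 24 completing it rest on an expected attrition of about 20%, not on length of participation or pay.
- *Pregnancy remarks.* In the illustration, a participant who conceives at week 10 is 18 − 10 = 8 to 19 − 10 = 9 weeks past conception when sessions end, so only earlier conceptions raise a question. An optional extension does not prevent referral after three months. The separate statement that the intervention adds no risk in pregnancy is not argued from the length of the study.

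**The case for a change.** The best case for acting is that both errors can be shown from the protocol's own figures and would be cheap to correct. The $260 matches neither a three-month study ($205) nor the fullest course the text allows ($300). It fits only someone paid for 24 weeks of contact checks who does not take the second assessment. The extension is not a remote possibility either, since anyone attending at the minimum frequency aimed for would qualify. And the word approximately cannot stretch 13 weeks to 24.

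Most of this stands as a description. The total is $40 short for those who extend, and the session extension contradicts the three-month maximum. What does not stand is the step from there to a change in the plan. The $40 is disclosed and itemised, so nothing is concealed, and nobody is paid more or less because the sum is wrong. There is no sign that the judgement of the payments as proportionate would change at $300. The pregnancy remarks may fail for some participants who extend, not for all of them.

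**Conclusion.** The inconsistencies are real but clerical. The compensation total is low by $40 (13% of $300), only for participants who take the optional second assessment and interview. The three-month maximum is exceeded by the session extension, to about week 18–19 if sessions are held every other week and then weekly. The 24 weeks of contact checks are ambiguous rather than contradictory.

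The statements on length of participation, including those that bear on pregnancy, do not agree and need reconciling for the record. I do not say which period is right, and I propose no clinical rule. Following the protocol as written gives the same participants, sessions, payments, assessments and benchmarks whichever sentence is later reworded, so no change to the design or the analysis follows.

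This rests on three months being about 13 weeks, on one contact check a week, and on the attendance patterns shown. The consent pages are not in the material available, so I draw no conclusion about what participants were told.

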### **Intervention and Assessments**

Following completion of the baseline assessment, the participant can meet with the PRS for up to 12 BA sessions (5 core content sessions and 7 review sessions) that can be scheduled based on individual treatment plans and particular participant needs based on distinct methadone dosing schedules, with the aim of a minimum session frequency of every other week. These sessions will be held either remotely or in-person at the drug treatment center, depending on participant availability and preference. Based on participant needs and preferences, the PRS may provide a second check-in between BA sessions. The additional check-in will focus on challenges and barriers that participants are experiencing in their methadone treatment. These sessions can be conducted via phone (including telephone, Zoom, or Google Voice), videoconference (Zoom), or in-person at the drug treatment center. Participants can conduct remote sessions from their homes or other preferred private locations. In-person sessions will take place at 1001 (the drug treatment center) and follow all UMDTC COVID-19 precautions for in-person interaction at this site.

The study interventionist will be a trained and supervised PRS who will receive training in protocol and intervention procedures. Supervision session between the PRS and a research team member (overseen by a licensed clinical psychologist on the research team) will take place approximately weekly. The peer hired as the study interventionist will be a Maryland Certified Peer Recovery Specialist (CPRS). CPRS certification is managed by Maryland Department of Health and requires 46 hours of training, 500 work hours in peer recovery support, and 25 hours of documented supervision under a registered peer supervisor.

Throughout the treatment program, the PRS will attempt to work with the patient approximately twice monthly (at a minimum). These sessions will occur in-person or via phone or over Zoom, a cloud-based video-conferencing system hosted by UMCP which allows for participants to call-in via phone or computer. Call administrators are able to record and store audio from a call on a local drive. Phone sessions will be recorded using Zoom or a hand-held recorder, in-person sessions will be recorded using a hand-held recorder, and all recordings will be saved to UMCP Box folder before they are deleted from the recording device. In order to further protect participant privacy, no audio recording will take place through a cloud platform. Sessions will be audio-recorded for supervision and to assess for treatment fidelity. This is noted in the consent process, and participants can refuse audio-recording at any time

(refusal of audio recording does not preclude participants from continuing to be part of the study). The PRS will reiterate before conducting each session that the audio-recording is for research purposes only, will not include any identifiable information, and will be kept confidential. Zoom security functions include a Waiting Room in which individuals can be screened before the call administrator allows them to join the call, and a Lock Meeting function which allows the administrator to block new participants from joining. Depending on different participants' needs, the timing of PRS meetings are expected to vary and will generally last up to half an hour to an approximate maximum of one hour. The PRS role is often flexible, particularly for patients who are poorly engaged in care. We will document how and when sessions take place (method of communication, locations of PRS and participants, time of day) to further our understanding of how the PRS role can optimize participant engagement in treatment.

In order to assess MOUD retention and treatment adherence, we will extract routinely-collected data from patient medical charts (maintained by UMDTC) at each BA session and assessment, with collected data consisting of MOUD intake date, clinic attendance, counselor appointments, dosing, dose volume, any notes on patient dosing, any breathalyzer results, any urinalysis or other drug testing results, and we will ask participants about any changes to their enrollment in treatment programs. This use of medical records is outlined in the consent form. At each BA session, participants will complete two items on the Ira Wilson's Self Report Adherence Measure.

During the approximately weekly or biweekly sessions, the PRS will determine the participants' specific circumstances and needs and will draw upon intervention components accordingly. Intervention components can include: Life Steps to identifying and overcoming day-to-day barriers to treatment, SMART goal identification and work, case management with the treatment facility, and modified Behavioral Activation (BA) to support retention in treatment. The PRS will complete/update the intake goals and follow-up goals with the participant during sessions to keep track of the participants' individual plans moving forward. PRS can also work through BA modules during sessions and review material as needed. After sessions, the PRS will complete a fidelity assessment to indicate which components were addressed. Specifically, the approach can focus on the following six elements: (1) psychoeducation regarding substance use, (2) treatment rationale, (3) identification of treatment barriers and solution planning, (4) identification of valued life areas to guide activity selection, (5) monitoring of current activities, (6) scheduling of new activities, and (7) tracking of actual behaviors and subsequent substance use behaviors.

If a participant misses BA sessions and/or dosing, the PRS will continue to follow up with the participant to assess barriers, concerns, and try to continue treatment.

Members of the research team may attend regularly scheduled UMDTC "teamlett" meetings held between the participant's counselor and attending physician at 1001. The purpose of these meetings is for the treatment team to review the patient's case and address any challenges faced in the treatment program. Research team attendance at these meetings will allow researchers to track the participant's engagement in the program, and may help inform how the intervention can further meet the participant's needs.

As part an effort to coordinate study enrollment with other IRB-affiliated research studies at the study site, the research team will share the enrollment status of participants with other IRB-affiliated researchers at the same study site. Researchers will be able to see participants' involvement in other

studies at this site. This information will be shared via a secure, central UMB-hosted server that is only accessible to other UMB IRB-affiliated researchers at the study site. No other participant information or study participation details will be shared.

With participant permission, all sessions will be audio recorded for supervision purposes and for fidelity assessments. A trained, independent rater will review approximately 20% of audio-recordings from sessions. The independent rater will fill out fidelity measures based on these session recordings for later comparison with the PRS's self-reported fidelity.

At the approximately 6-week and approximately 3-month follow-ups, a trained member of the research team will complete remote or in-person (depending on participant availability and preference) assessments with the participant. We anticipate that phone or video-based assessments may need to be shorter than in-person assessments; thus, we have streamlined and reordered our assessment measures to prioritize the most important measures for this study. This will allow us to gather the most important data earliest during the remote assessments in case a participant experiences difficulties with technology or is unable to continue the remote assessment for some other reason (such as a family emergency). The approximately 6-week midpoint assessment will be a brief assessment of factors that we hypothesize may change during the course of the intervention. Measures that can be used in this assessment include Treatment Program Status, MOUD Adherence and Retention: Chart Extraction, Ira Wilson's Self-Report Adherence Measure, Barriers to Adherence of Medication for Opioid Use, Short Inventory of Problems-Revised, TLFB, Patient Health Questionnaire-9, Substance Use Stigma Mechanisms Scale, Methadone-Maintenance Treatment Stigma Mechanisms Scale, Behavioral Activation for Depression Scale or Behavioral Activation for Depression Scale-Short Form, and the Reinforcement-Punishment Inventory or the Environmental Reward Observation Scale. The posttreatment assessment measures can include the same measures as the baseline assessment with the exception of no Demographic and other Characteristics Questionnaire and no MINI psychosis and mania modules. The posttreatment assessment can also include the Treatment Program Status form and the JHU Feasibility and Acceptability measure. The JHU Feasibility and Acceptability measure assesses for the participant's satisfaction with working with the PRS and important barriers and facilitators to implementation of the intervention.

After completing the posttreatment assessment (approximately 3 months after baseline), participants will be invited to complete a qualitative exit interview which will ask them about their experience in the treatment. Exit interview can take place by phone, video, or in-person. Participants who have dropped out of the program early will also be invited to complete the midpoint assessment, posttreatment assessment, and exit interview over the remaining period of the planned study timeframe (an intent-to-treat approach) or at their earliest convenience. The exit interview will take place immediately following the posttreatment assessment or may be scheduled within approximately one week. Because this interview will ask about the participants' experiences with the PRS, the interview will be conducted by a trained member of the study staff and the participants' responses will not be shared with the PRS. The participant will be asked for their consent for the interview to be recorded. They will be assured that audio recording will be used for research purposes only. The recording will be uploaded to UMCP's Box folder immediately following the session, and the audio file will be deleted from the recording device.

As stated above, posttreatment assessment will take place at approximately three months after baseline, at which point participants who have not yet completed 12 intervention sessions may choose to continue meeting with the interventionist approximately weekly until they reach a maximum of 12 sessions or until they choose to discontinue intervention (whichever occurs first). Those participants will be offered another, optional posttreatment assessment and exit interview, also compensated with \$25 and \$15 gift cards (respectively).

It will take approximately 30-60 minutes to complete the baseline assessment, approximately 15-30 minutes to complete the midpoint assessment, approximately 30-60 minutes to complete the posttreatment assessment, and approximately 30 minutes to complete the posttreatment exit interview. The participant will receive \$25 (gift certificate) for completing the baseline, \$15 for completing the abbreviated midpoint assessment, a \$25 gift certificate for completing the posttreatment assessment, and \$15 for completing the exit interview. Compensation for the baseline and posttreatment assessments may be broken up into more than one day (\$10 gift card for completing the first day of the assessment and \$15 gift card for completing the remainder of the assessment) if the assessment is paused and resumed another day for any reason. Participants may receive physical gift cards or e-gift cards via email, text, mail, or may pick up their gift cards through a no-contact method at UMDTC. Researchers will coordinate with UMD and UMDTC to determine an acceptable method of remote payment delivery to participants without direct social contact between researcher team and participants.

We recognize that meeting with participants remotely or in person may both present new challenges to participation, including cost associated with using their own device for session contact or cost of attending sessions when not scheduled for dosing. We also understand that participants may also face additional transportation costs when presenting in-person to the drug treatment center during COVID-19. As such, participants will receive compensation in the form of gift cards for each session attended to cover transportation and/or telecommunication costs. Gift cards of \$5 per session will be provided to participants after each session attended for the duration of the study. Total gift card compensation for intervention session attendance (above the compensation for assessment participation) will have a maximum of \$60, reflecting attendance of 12 maximum sessions.

During this period when telecommunications are heavily relied upon due to COVID, it is increasingly important to ensure that patient contact details are up-to-date. In order to promote uninterrupted communications between researchers and participants and improve retention and tracking of a hard-to-retain sample, we will provide incentives for participants to confirm their contact details. Participants will receive \$5 gift cards for each week that they confirm their up-to-date contact details. These gift cards will be provided after each contact verification, with a total possible amount of \$120 if the participant contacts the research team weekly for up to 24 weeks of the study.

For any remote call with the participant, the research team will document the participant ID number, researcher name, location of research team member, location of participant, means used (telephone or computer), start and end time, quality of call (excellent, minor issues, significant impediment), and any barriers to effective communication in a database. For any in-person session (assessment or intervention session), researchers will follow procedures outlined in the IRB-approved in-person human subjects protocol.

